7.3.6 Gynaecological Examination

A complete gynaecological examination will be performed at screening and end-of-trial. Information will be recorded for breast, external genitalia, vagina, cervix, uterus, ovaries and fallopian tubes.

At screening, each category will be evaluated as normal, abnormal not clinically significant or abnormal clinically significant. Abnormal clinically significant findings at screening must be reported as medical history or as reason for infertility on the Infertility History form, as applicable, and evaluated in accordance with inclusion criteria 7 (Section 4.1.1).

At end-of-trial, potential changes from screening to end-of-trial will be evaluated for each category. In case of changes, these will be evaluated as normal, abnormal not clinically significant or abnormal clinically significant. Abnormal clinically significant changes from screening to end-of-trial must be recorded as adverse events.

7.3.7 Serum Concentrations of AMH, TSH, and Prolactin

A blood sample will be drawn at screening to evaluate circulating AMH, TSH, and prolactin concentrations.

The analysis will be performed at a central laboratory. The investigator will review and evaluate the laboratory results. The laboratory report will be signed and dated by the investigator.

7.3.8 Clinical Chemistry and Haematology Parameters

Blood samples will be drawn at screening and end-of-trial to evaluate clinical chemistry and haematology parameters.

CHEM-20: alanine transaminase, albumin, alkaline phosphatase, aspartate aminotransferase, bicarbonate, bilirubin direct, bilirubin total, blood urea nitrogen, calcium, chloride, cholesterol total, creatinine, gamma-glutamyl transpeptidase, glucose, lactate dehydrogenase, phosphorus, potassium, sodium, total protein, and uric acid.

Complete Blood Count (CBC): red blood cells, red blood cell morphology, white blood cells, white blood cell morphology, haemoglobin, haematocrit, mean corpuscular volume, mean corpuscular haemoglobin, mean corpuscular haemoglobin concentration, and platelets.

The analysis will be performed at a central laboratory. The investigator will review the laboratory results, evaluate and document whether any abnormal results are non-clinically or clinically significant. The Laboratory Report will be signed and dated by the investigator.

7.3.9 Ovarian Volume

As part of the transvaginal ultrasounds performed at stimulation day 1 and end-of-stimulation, the size of each ovary will be measured. Length, width, and depth will be recorded in mm. The measures will be used for calculation of ovarian volume.

7.3.10 Endometrial Status

Transvaginal ultrasound of the uterus to assess the endometrial status will be conducted on stimulation days 1 and 6 and thereafter at least every second day during the stimulation period. The endometrial status assessments consist of the following parameters: endometrial thickness, endometrial triple-layer structure and endometrial echogenicity pattern [*note*: the latter two are not assessed on stimulation day 1].

Endometrial thickness (composed of both layers of the endometrium) will be measured in the sagittal view of the uterus from the proximal and distal interfaces between the echogenic endometrium and the hypoechoic inner layer of the myometrium. Care should be taken not to include the hypoechoic subendometrial halo and to account for the presence of any fluid in the uterine cavity (not to be included in the endometrial thickness value). Endometrial thickness will be recorded in mm.

Endometrial triple-layer structure will be recorded as observed or not.

Endometrial echogenicity pattern will be recorded as hypoechoic, isoechoic, hyperechoic, or not possible to evaluate.

7.3.11 Embryo Transfer Procedure

Any difficulty or eventuality (e.g. greater resistance is met, the procedure is time-consuming, there is a need to change to a harder catheter, uterine sounding or cervical dilation is carried out, or there is blood in any part of the catheter) during the transfer procedure will be noted.

7.3.12 Concomitant Medication

The use of any concomitant medication within the last 3 months prior to informed consent for participation in the trial (except medication used in previous infertility treatment cycles) and throughout the trial will be recorded. Recording of concomitant medication will be performed at all visits. Any changes in concomitant medications or treatments must be recorded at each visit.

7.3.13 Drug Dispensing and Accountability

For all medicinal products, dates of administration and dose administered will be recorded. Furthermore, time of administration will also be recorded for IMP, GnRH agonist, and hCG. Details on drug dispensing and accountability are provided in Section 5.1.

7.4 Pregnancy Follow-up

7.4.1 Live Birth Rate

For subjects with an ongoing pregnancy, information on the pregnancy period, including any relevant interventions performed and incidence of second or third trimester losses, as well as the pregnancy outcome, e.g. live birth^c, will be collected.

7.4.2 Neonatal Health

Neonatal health data will be collected at birth and at 4 weeks after birth for all children born. At birth, the data collected will include gender, birth weight and length, way of delivery, position of neonate and Apgar score as well as information on any congenital anomalies and admission to neonatal intensive care unit (NICU) or neonatal care unit (NCU). At 4 weeks after birth, the data collected will include any congenital anomalies, hospitalisations, death of neonate and important medical events. These follow-up data can be obtained from the subject, unless medical judgement is required.

^c Live birth: gestational age \geq 24 weeks + 0 days, calculated from the day of day 3 embryo transfer + 17 days

7.5 Handling of Biological Samples

A trial-specific laboratory manual will be provided to the participating sites, describing in detail how to handle, store, and transport biological samples in this trial. For biological samples collected in the trial, analyses beyond those described in the protocol can only be performed after obtaining required approvals. The processes related to handling of biological samples will be described in the Informed Consent Forms and biobank / data protection legislation, including local legislation, will be adhered to.

Blood and urine samples collected for local laboratory analyses will be destroyed after the analysis. Blood samples collected for central laboratory analyses will be maintained in storage after the end of the trial. Destruction will take place within 2 years after reporting of the trial.

8 ADVERSE EVENTS

8.1 Adverse Event Definition

An adverse event is any untoward medical occurrence in a subject participating in a clinical trial. It includes:

- Any unfavourable and unintended sign, symptom or disease temporally associated with the use of the IMP, whether or not considered to be caused by the IMP.
- Adverse events commonly observed and adverse events anticipated based on the pharmacological effect of the IMP.
- Any laboratory abnormality, vital sign or finding from physical or gynaecological examination assessed as clinically significant by the investigator [*note*: pre-existing conditions diagnosed through assessments and examinations at the screening visit or during the screening period are not adverse events but are recorded as medical history].
- Accidental injuries, reasons for any change in medication (drug and/or dose), reasons for any medical, nursing or pharmacy consultation, or reasons for admission to hospital or surgical procedures.

All adverse events will be coded by Ferring Global Pharmacovigilance using Medical Dictionary for Regulatory Activities (MedDRA; the version effective at trial start).

8.2 Collection and Recording of Adverse Events

8.2.1 Collection of Adverse Events

The investigator must monitor the condition of the subject throughout the trial from the time of obtaining informed consent until the last visit; the last scheduled visit or a separate end-of-trial visit scheduled within 7 days of the last scheduled visit or at least 9 days after the end-of-stimulation visit (applicable to subjects who undergo triggering of final follicular maturation).

The sources of adverse events cover:

- The subject's response to questions about her health (a standard non-leading question such as "How have you been feeling since your last visit?" is asked at each visit).
- Symptoms spontaneously reported by the subject.
- Investigations and examinations where the findings are assessed by the investigator to be clinically significant changes or abnormalities.
- Other information relating to the subject's health becoming known to the investigator (e.g. hospitalisation).

8.2.2 Recording of Adverse Events

The investigator must record all adverse events in the Adverse Event Log provided for each subject in the EDC system with information about:

- Adverse event description
- Date and time of onset (time can be omitted, if applicable) [*note:* if date of onset of an event is the same as the date of informed consent or date of IMP administration, time is important and should not be omitted]
- Intensity
- Causal relationship to IMP
- Action taken to IMP
- Other action taken
- End date and time (time can be omitted, if applicable)
- Outcome
- Seriousness

Each of the items in the Adverse Event Log is described in detail in the following sections.

Adverse Event Description

Adverse events should be recorded as diagnoses, if available. If not, separate signs and symptoms should be recorded. One diagnosis/symptom should be entered per record.

If a subject suffers from the same adverse event more than once and the subject recovers in between the events, the adverse events should be recorded separately. If an adverse event changes in intensity, a worst-case approach should be used when recording the event, i.e. the highest intensity and the longest duration of the event.^d If a subject suffers from a pre-existing medical condition that worsens in intensity after signed informed consent, it should be recorded as an adverse event [*Note:* a procedure is not an adverse event; the reason for conducting the procedure is, hospitalisation is not an adverse event; the reason for hospitalisation is, death is not an adverse event, but the cause of death is (an exception is sudden death of unknown cause, which is an adverse event)].

^d Exception: if an adverse event with onset before the first IMP administration (i.e. a pre-treatment adverse event) worsens in intensity after IMP administration, this must be recorded as two separate events. The initial adverse event should be recorded with outcome “not recovered”, without recording end date and time. The second adverse event should be recorded with date and time of onset when the intensity changed.

Date and Time of Onset

The date of onset is the date when the first sign(s) or symptom(s) were first noted. If the adverse event is an abnormal clinically significant laboratory test or outcome of an examination, the onset date is the date the sample was taken or the examination was performed.

Intensity

The intensity of an adverse event must be classified using the following 3-point scale:

Mild: Awareness of signs or symptoms, but no disruption of usual activities

Moderate: Disruption of usual activities (disturbing)

Severe: Inability to work or perform usual activities (unacceptable)

Causal Relationship to IMP

The possibility of whether the IMP caused the adverse event must be classified as one of the following:

Reasonable possibility:

There is evidence or argument to suggest a causal relationship between the IMP and the adverse event. The adverse event may occur as part of the pharmacological action of the IMP or may be unpredictable in its occurrence.

Examples:

- Adverse events that are uncommon but are known to be strongly associated with IMP exposure.
- Adverse events that are not commonly associated with IMP exposure, but the event occurs in association with other factors strongly suggesting causation, such as a strong temporal association or the event recurs on rechallenge.

No reasonable possibility:

There is no reasonable evidence or argument to suggest a causal relationship between the IMP and the adverse event.

Examples:

- Known consequences of the underlying disease or condition under investigation.
- Adverse events common in the trial population, which are also anticipated to occur with some frequency during the course of the trial, regardless of IMP exposure.

An adverse drug reaction is defined as an adverse event assessed to be causally related to the administration of IMP with a reasonable possibility.

Action Taken to IMP

The action taken to the IMP in response to an adverse event must be classified as one of the following:

- No change (applicable for when the IMP regimen is maintained as well as for adverse events occurring before first dose of IMP or after last dose of IMP as per protocol)
- Discontinued
- Interrupted
- Dose reduced
- Dose increased

Other Action Taken

Adverse events requiring therapy must be treated with recognised standards of medical care to protect the health and well-being of the subject. Appropriate resuscitation equipment and medicines must be available to ensure the best possible treatment of an emergency situation.

If medication is administered to treat the adverse event, this medication should be entered in the Concomitant Medication Log.

End Date and Time

The date and time (time can be deleted/omitted, if applicable) the subject recovered or died.

Outcome

The outcome of an adverse event must be classified as one of the following:

- Recovered (fully recovered or the condition has returned to the level observed at initiation of trial treatment)
- Recovered with sequelae (resulted in persistent or significant disability/incapacity)
- Recovering (the event is improving)
- Not recovered
- Fatal

8.3 Other Significant Adverse Events

8.3.1 Adverse Events Leading to Discontinuation

Adverse events leading to discontinuation from the trial, discontinuation from treatment, or dose reduction not defined in the clinical trial protocol will be considered as other significant adverse events.

8.3.2 Adverse Event of Special Interest

8.3.2.1 Ovarian Hyperstimulation Syndrome

Symptoms and Classification

OHSS is an adverse event of special interest during controlled ovarian stimulation. Investigators will record OHSS symptoms and use these symptoms directly to grade (1, 2, 3, 4 or 5) each OHSS case into Golan's classification system³⁸ as shown in [Table 8-1](#).

Table 8-1 Classification of Mild, Moderate and Severe OHSS (Golan's Classification System)

Mild OHSS	
Grade 1	Abdominal distension and discomfort
Grade 2	Features of grade 1 plus nausea/vomiting and/or diarrhoea. Ovaries enlarged to 5-12 cm. ^{a)}
Moderate OHSS	
Grade 3	Features of mild OHSS plus ultrasonic evidence of ascites. ^{b)}
Severe OHSS	
Grade 4	Features of moderate OHSS plus clinical evidence of ascites and/or hydrothorax (or breathing difficulties). Paracentesis due to OHSS symptoms. ^{c)}
Grade 5	All of the above plus change in blood volume, increased blood viscosity due to haemoconcentration, coagulation abnormalities, and diminished renal perfusion and function. ^{d)} Hospitalisation due to OHSS symptoms.

^{a)} For each ovary, the size will be the average of the greatest diameter and its greatest perpendicular diameter. Ovarian enlargement will be based on the average size of the right and left ovaries. The sizes of both ovaries should be recorded.

^{b)} For subjects with transvaginal evidence of ascites, the size of the fluid pockets in the pelvis (Douglas pouch, vesico-uterine pouch, etc) should be estimated by measuring the greatest diameter and its greatest perpendicular diameter and multiplying these two numbers (the unit will be cm²). Peritoneal fluid is the total size of all fluid pockets in the pelvis.

^{c)} In case of paracentesis, the volume of fluid drained should be measured.

^{d)} Haemoconcentration is defined as haematocrit >45 %. Electrolyte disturbances is defined as hyponatremia (sodium <135 mEq/L) and/or hyperkalemia (potassium >5.0 mEq/L). Coagulation abnormalities are defined as presence of thromboembolic events, abnormal prothrombin time or abnormal activated partial thrombin time. Diminished renal perfusion is defined as creatinine >1.2 mg/dL. Oliguria is defined as urine output less than 500 mL / 24 hours. Anuria is defined as failure to produce urine. If applicable, actual volume of urine output will be recorded.

All cases of OHSS must be reported as adverse events. Those that fall under the category serious adverse events (SAEs) must be reported as such [Note: the classification 'mild OHSS', 'moderate OHSS' and 'severe OHSS' does not refer to the classification of an adverse event's intensity (also rated mild, moderate, or severe)].

Subject narratives will be prepared for all moderate and severe OHSS cases.

Concerning timing, early OHSS will be defined as OHSS with onset \leq 9 days after triggering of final follicular maturation and late OHSS will be defined as OHSS with onset $>$ 9 days after triggering of final follicular maturation.

All OHSS cases will be monitored on an ongoing basis and discussed at centralised monitoring meetings, as described in the centralised monitoring plan.

Investigations to be Conducted in Subjects where OHSS Symptoms are Observed

The following investigations must be conducted when OHSS symptoms are first observed and repeated when there are clinically relevant changes in the OHSS presentation:

- Body weight and maximum abdominal circumference (for all OHSS)
- Vital signs (for all OHSS)
- Blood sample for central laboratory analysis of (for moderate/severe OHSS):
 - Estradiol and progesterone
 - CHEM-20 (alanine transaminase, albumin, alkaline phosphatase, aspartate aminotransferase, bicarbonate, bilirubin direct, bilirubin total, blood urea nitrogen, calcium, chloride, cholesterol total, creatinine, gamma-glutamyl transpeptidase, glucose, lactate dehydrogenase, phosphorus, potassium, sodium, total protein, uric acid)
 - CBC (red blood cells, red blood cell morphology, white blood cells, white blood cell morphology, haemoglobin, haematocrit, mean corpuscular volume, mean corpuscular haemoglobin, mean corpuscular haemoglobin concentration, platelets)
 - Coagulation parameters (prothrombin time, activated partial thrombin time)

Any treatments of OHSS, e.g. intravenous administration of volume expanders, paracentesis, use of low-molecular-weight heparin and intravenous administration of albumin, must be recorded as concomitant medication.

8.3.2.2 Pregnancy Losses

The following terminology should be used for reporting of pregnancy losses during the trial:

Biochemical pregnancy:	Positive β hCG test but no gestational sac is observed on later transvaginal ultrasound, or menstruation is reported
Spontaneous abortion:	Positive β hCG test but all intrauterine gestational sacs are without fetal heart beat as documented by ultrasound, or there are no viable fetuses observed by ultrasound
Vanishing twin:	Spontaneous disappearance of an intrauterine gestational sac with or without heart beat in a pregnancy where one viable fetus remains as documented by ultrasound

Ectopic pregnancy: Extrauterine gestational sac with or without fetal heart beat as documented by ultrasound or surgery

Concerning timing, a pregnancy loss occurring before ongoing pregnancy (i.e. during 1st trimester) will be defined as an early pregnancy loss, while a pregnancy loss occurring after ongoing pregnancy (i.e. during 2nd or 3rd trimester) during the pregnancy follow-up will be defined as a late pregnancy loss.

8.3.3 Local Tolerability

Injection site reactions after administration of IMP are only to be reported as adverse events if they require active management, i.e. discontinuation of IMP, additional investigations or treatment of the injection site reaction.

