The most frequently reported adverse drug reactions during treatment with FE 999049 are headache, pelvic discomfort, ovarian hyperstimulation syndrome (OHSS), pelvic pain, nausea, adnexa uteri pain and fatigue.¹ OHSS is an intrinsic risk of the ovarian stimulation. Known gastrointestinal symptoms associated with OHSS include abdominal pain, discomfort, and distension, nausea, vomiting, and diarrhoea. Ovarian torsion and thromboembolic events are known to be rare complications of ovarian stimulation treatment.

GONAL-F is a commercially available rFSH preparation with established safety and efficacy. The most frequent adverse events in relation to use of GONAL-F are as follows: headache, ovarian cysts and injection site reactions (all reported as very common, i.e. $\geq 10\%$) and abdominal pain, abdominal distension, abdominal discomfort, nausea, vomiting, diarrhoea and mild or moderate OHSS including associated symptomatology (all reported as common, i.e. 1% to $< 10\%$).²⁰ The GONAL-F dosing regimen used in this trial is in line with labelling recommendations.

The most serious risk associated with gonadotropin treatment is OHSS. OHSS manifests itself with increasing degrees of severity. Moderate / severe OHSS is associated with marked ovarian enlargement, fluid accumulation and other complications. In patients treated with a GnRH agonist protocol, early OHSS can be prevented by withholding gonadotropins or withholding human chorionic gonadotropin (hCG). Very rare cases of serious allergic reactions have been reported after injection of gonadotropins.

Trial Procedures and Concomitant Fertility Medications

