2 TRIAL OBJECTIVES AND ENDPOINTS

2.1 Objectives

Primary Objective

- To compare FE 999049 at a starting dose of either 10 µg or 15 µg to GONAL-F at a starting dose of either 150 IU or 225 IU in conventional regimens with respect to ovarian response in women undergoing controlled ovarian stimulation in a long GnRH agonist protocol

Secondary Objectives

- To compare the follicular development, endocrine profile and embryo development associated with conventional dosing of FE 999049 and GONAL-F
- To compare the treatment efficiency associated with conventional dosing of FE 999049 and GONAL-F
- To compare the safety profile associated with conventional dosing of FE 999049 and GONAL-F

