9.7 Safety – Adverse Events

Adverse events will be coded using MedDRA. Treatment-emergent adverse events^g will be summarised by System Organ Class (SOC) and Preferred Term (PT).

^g A treatment-emergent adverse event is any adverse event occurring after start of IMP and until the last scheduled visit (or alternatively at a separate end-of-trial visit within 7 days of the last scheduled trial visit), or a pre-treatment adverse event or pre-existing medical condition that worsens in intensity after start of IMP and until the end-of-trial visit.

Adverse events and other safety assessments will be evaluated using descriptive statistics. For OHSS, see Section [9.6.3](#).

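### Injection site reactions that need no active management are left out of the adverse-event data, so the by-arm safety table cannot inform on overall local tolerability

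*Combined protocol and SAP*

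**What the plan says.** Section 8.1 defines an adverse event broadly, starting with "Any unfavourable and unintended sign, symptom or disease temporally associated with the use of the IMP", and sets no threshold of severity or management. Section 8.2.2 then states: "The investigator must record all adverse events in the Adverse Event Log". Its 3-point intensity scale has a mild grade for events that do not disturb usual activities.

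Section 8.3.3 carves out one event: injection site reactions "are only to be reported as adverse events if they require active management, i.e. discontinuation of IMP, additional investigations or treatment" of the reaction. No reason is given.

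Section 1.3 lists among the most frequent events with GONAL-F "headache, ovarian cysts and injection site reactions (all reported as very common", a category it defines as 10% or more. One of the secondary objectives in 2.1 is "To compare the safety profile associated with conventional dosing of FE 999049 and GONAL-F". Section 9.7 summarises treatment-emergent events by system organ class and preferred term, and adds: "Adverse events and other safety assessments will be evaluated using descriptive statistics".

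**The concern.** The two products come in different pens and are injected daily for up to 20 days, so reactions at the injection site are an expected part of their safety profiles. Under 8.3.3 a reaction that is felt or seen but needs no action is not recorded. Section 2.2 has no local-tolerability endpoint. Sections 7.2 and 7.3, the flow chart in 6.1 and the source-data list in 10.1 contain no injection-site assessment. The 30-minute observation after the first IMP dose (6.5.1) emphasises acute allergic reaction. An unmanaged reaction is therefore lost.

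What is at stake is one component of the secondary safety objective. The table will understate injection site reactions in both arms by design. Because the rule is the same in both arms, it favours neither, but it removes most of the information on this event if few reactions are managed.

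**Working it through.** **The plan's own figures.** The protocol gives none for local tolerability. Its only sample-size figure is for the primary endpoint: 2 × (7.5 × (1.960 + 1.282) / 3)² = 131.3, so 132 per group against the stated 133. That reproduces closely, and nothing below depends on it.

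**Inputs**
- Subjects per arm: 150 (section 3.2).
- Reaction rate with GONAL-F: 10%, the floor of the very common category (section 1.3).
- Share of reactions actively managed: not in the documents. Assumed 5%, 10% and 20%.
- Comparison rates of 3% and 5% in the other arm: not in the documents; purely illustrative.

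**Step 1: reactions expected.** 150 × 0.10 = 15 GONAL-F women at the floor, more if the true rate is higher.

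**Step 2: reactions recorded under 8.3.3.** Expected count = 15 × managed share. Chance of no recorded case in the arm = (1 − 0.10 × share)^150.

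| Managed share (assumed) | Expected recorded | Chance of none recorded |
|---|---|---|
| 5% | 0.75 | 47% |
| 10% | 1.5 | 22% |
| 20% | 3.0 | 5% |

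**Step 3: what a real difference would look like.** Suppose true rates of 10% and 3%, and the same managed share in both arms. The 7-point difference then appears as 7 × share: 0.35 points at 5%, 0.7 at 10% and 1.4 at 20%.

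**Step 4: what full recording would give.** With 10% in both arms, the 95% half-width for the difference is 1.96 × √(2 × 0.10 × 0.90 / 150) = 0.068, or about 6.8 percentage points. As a gauge of information only, since no test is planned, the power of a two-sided 5% Fisher exact test with 150 per arm is:
- about 63% for 10% against 3%;
- about 30% for 10% against 5%.

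Full recording would thus describe local tolerability in each arm, but would reliably separate the arms only if the difference were large.

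**The case against.** **A stated choice, applied equally.** Section 8.3.3 is an explicit rule under its own heading, and 8.3.4 limits the reporting of menstrual bleeding in a similar way. A specific rule may narrow a general definition, so this is not an internal contradiction. That stands. The point is what the rule costs the safety objective.

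**No planned comparison is broken.** Local tolerability is not an endpoint, and adverse events are only described. That also stands, and the power figures above do not stand for a planned test.

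**No product difference is shown.** A reader might infer from 1.3 that the products differ, because injection site reactions appear in the GONAL-F list and not in the FE 999049 list. The documents do not support this. The FE 999049 list cites the Investigator's Brochure and gives adverse drug reactions without frequencies. The GONAL-F list cites the product label and gives adverse events in frequency bands. Absence from the first list is not evidence of a lower rate.

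**Attribution.** Every woman also injects triptorelin subcutaneously each day through stimulation (5.1.2), with timing to be aligned with the IMP (6.3, 6.5.1). Section 1.3 names injection site reactions among the frequent events of the concomitant medications. Some mild reactions will be hard to assign to the IMP. This stands, and any fix has to deal with it.

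**Blinding and reporting bias.** Women know their allocation and are told not to reveal it to the investigator, who records adverse events. Unblinding of an assessor is a major deviation that removes data from the per-protocol set (9.3). This argues against new questioning about pens or products. It does not argue against keeping what women already volunteer: 8.2.1 has a standard non-leading question at each visit, and other subject-reported events carry the same open-label weakness.

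**Conclusion.** The concern holds as a limitation on the secondary safety objective. The 9.7 table will cover actively managed injection site reactions only and cannot inform on overall local tolerability. At the 10% floor, about 15 GONAL-F women would have a reaction and about 0.75 to 3 would be recorded. The 15 rests on the protocol's own category; the recorded count rests wholly on the assumed 5% to 20% managed share.

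Two stronger readings go too far. A reader might conclude that local tolerability cannot be compared at all, but managed reactions are still recorded and tabulated in both arms, though probably in numbers too small to inform. A reader might also expect the sparse table to be presented as proof of equal tolerability, but no section says so. The primary analysis, the OHSS endpoint and serious adverse event reporting are not affected.

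**What to change.** Amend 8.3.3 so that a reaction at the IMP injection site is logged as an adverse event if the subject volunteers it at the existing non-leading question or site staff note it. Use the existing 3-point intensity scale and add a flag for active management. Where possible, record whether the site was used for the IMP or for triptorelin. Staff should not ask about the product or pen, so that assessor blinding is kept.

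In 9.7, tabulate all reactions and actively managed reactions by arm, descriptively. State with the table that subjects know their allocation and inject triptorelin daily, with timing aligned to the IMP.

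If the sponsor keeps the present rule, the minimum is a sentence in 8.3.3 and 9.7 saying that reported rates cover actively managed reactions only and that overall local tolerability is not compared.

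The cost is protocol wording and some extra log entries: about 15 in the GONAL-F arm at the 10% floor with one entry per affected woman, and more if rates are higher or reactions recur. The remaining weakness is open-label reporting, which the caveat discloses but does not remove.
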